6.1.5 Storage

All study medication will be kept in a secure place under appropriate storage conditions in the Pharmacy Department at the Royal Infirmary of Edinburgh.

6.2 PLACEBO

Astra Zeneca will supply a matched placebo in prefilled HDPE bottles with Child resistant caps. The placebo will then be labelled by ISG and released to the Pharmacy Department at the Royal Infirmary of Edinburgh.

6.3 DOSING REGIME

One tablet twice daily for 12 months.

6.4 DOSE CHANGES

No alteration in the planned dosing regime will be allowed.

6.5 PARTICIPANT COMPLIANCE AND ACCOUNTABILITY

Members of the research team will assess treatment compliance at attendance of each of the study visits by interview and pill count. Non-compliance with the dosing regime will only be considered a protocol deviation if the participant takes less than 90% of the planned dose. Any unused study medication will be returned to the Pharmacy Department at the Royal Infirmary for destruction.

6.6 OVERDOSE

Ticagrelor is well tolerated in single doses up to 900 mg. Gastrointestinal toxicity was dose-limiting in a single ascending dose study. Other clinically meaningful adverse reactions which may occur with overdose include dyspnoea and ventricular pauses.

In the event of overdose, we will observe for these potential adverse reactions and consider ECG monitoring. There is currently no known antidote to reverse the effects of ticagrelor and it is not expected to be dialysable. Treatment of overdose will follow local standard medical practice. The expected effect of excessive ticagrelor dosing is prolonged bleeding risk associated with platelet inhibition. If bleeding occurs appropriate supportive measures will be taken.

If an overdose occurs in the course of the study, the investigators or other site personnel will inform appropriate AstraZeneca representatives **within one day**, ie, immediately but no later than **the end of the next business day** of when he or she becomes aware of it.

The designated AstraZeneca representative will work with the investigator to ensure that all relevant information is provided to the AstraZeneca Patient Safety data entry site.

6.7 OTHER MEDICATIONS

6.7.1 Non-Investigational Medicinal Products

18F-Sodium Fluoride (18F-NaF)

At the time of positron emission tomography and computed tomography coronary angiography, patients may receive oral and/or intravenous beta-blockade, such as metoprolol 5-100 mg, to slow the heart rate to below 65 beats per minute to maximise image quality and reduce radiation exposure. Glyceryl trinitrate spray or tablet will be administered sublingually (200-400 µg) to induce coronary vasodilatation to enhance image quality of the coronary angiogram.

6.7.2 Permitted Medications

All patients will be maintained on aspirin 75 mg once daily and maximally tolerated dose of statin. Patients will be encouraged to be maintained on maximally tolerated doses of angiotensin-converting enzyme inhibition and beta-blocker therapy as clinically indicated and

in accordance with local guidelines. Following completion of the study, the trial medications will be discontinued.

6.7.3 Prohibited Medications

- Strong CYP3A4 inhibitors, such as ketoconazole, clarithromycin, nefazodone, ritonavir, atazanavir. Thienopyridines such as prasugrel, clopidogrel and ticlopidine
- Coumarin anticoagulants such as warfarin
- Direct thrombin inhibitors such as dabigatran
- Factor Xa inhibitors such as rivaroxaban and apixaban
- Ergot alkaloids
- Cisapride
- Simvastatin or lovastatin when taken at doses >40 mg daily

7 STUDY ASSESSMENTS

Trial participants will undergo 8 study visits: screening visit, baseline, randomisation and after 1, 3, 6, 9 and 12 months.

7.1 SAFETY ASSESSMENTS

The study does not have any pre-specified safety outcome measures. However, all bleeding events will be categorized according to the previous PLATO criteria [Wallentin *et al*, 2009]. These will be reported through adverse event reporting mechanisms (see Section 10).

7.2 STUDY ASSESSMENTS

This is a prospective single-centre randomized double blind matched placebo controlled trial of ticagrelor 90 mg twice daily in patients with stable coronary artery disease for 1 year. Subjects will attend for clinical assessments at 30 days, 3, 6, 9 and 12 months with a final computed tomography coronary angiogram at the end of the study. The randomisation visit must be conducted within 25 days of the baseline visit.

	Screening -183 days	Baseline (-15 days ±10 days)	Randomisation (Day 0)	30 days (±5 days)	3 months (±14 days)	6 months (± 14 days)	9 months (± 14 days)	1 year (± 14 days*)
Eligibility Criteria and PIS	X							
Continuing eligibility confirmed			X	X	X	X	X	
Consent	X							
Concomitant medications		X		X	X	X	X	X
Clinical History		X		X	X	X	X	X
Physical Examination		X						
Clinical Biochemistry and haematology	X (if not checked in past 6 months)	X					X	
Blood sampling for hsTnI		X		X	X	X	X	X
Blood sampling for PMA		X		X				
12-lead ECG		X		X	X	X	X	X
AE/SAE Reporting		X		X	X	X	X	X
Treatment allocation/Medication dispensed			X		X	X	X	
Compliance check				X	X	X	X	X
18F-Fluoride PET		X	X		X	X		X
			Additional 18F-Fluoride PET scans will be performed in a subgroup only					
CT attenuation correction								
			CT attenuation correction is required prior to each PET scan for the subgroups who undergo this					
CT Calcium Score		X						X
CT Coronary Angiogram		X	Repeat CTCA scans will be performed at the time of each PET scan for those who are in the reproducibility and natural history sub-studies					X*

* Where it is not possible for the CT scan at the 1 year visit to be performed at the same time as the other 1 year study assessments participants may be asked to attend an additional visit during which the CT scan will be performed. In this situation the remainder of the study assessments will be performed within the planned visit window (± 14 days) and the CT scan will be arranged for the earliest practicable opportunity.

7.2.1 Baseline Assessments

Baseline assessments will include clinical history and examination, review of patient records to confirm study eligibility and record clinical profile, standard clinical biochemical and haematological variables, plasma high sensitivity cardiac troponin I measurement, platelet-monocyte aggregates, 12-lead electrocardiogram, 18F-fluoride positron emission tomography,

computed tomography coronary calcium score and angiography, and storage of plasma, serum and DNA for future analysis.

7.2.2 Follow Up Assessments

At 1, 3, 6, 9 and 12 months, participants will undergo repeat clinical assessment, blood sampling, and 12-lead electrocardiogram. Compliance will be recorded by patient history and tablet count by a delegated member of the research team. At the final study visit (12 months), subjects will also undergo a repeat computed tomography coronary calcium score and angiography.

Where it is not possible for the CT scan at the 12 month visit to be performed at the same time as the other 12 month study assessments participants may be asked to attend an additional visit during which the CT scan will be performed. In this situation the remainder of the study assessments will be performed within the planned visit window (\pm 14 days) and the CT scan will be arranged for the earliest practicable opportunity.

7.2.3 High Sensitivity Cardiac Troponin I

Plasma cardiac troponin I concentrations will be measured by the accredited Clinical Biochemistry Department of the Royal Infirmary of Edinburgh using the ARCHITECT_{STAT} high-sensitive troponin I assay (Abbott Laboratories, Abbott Park, IL). This is the first commercially available high-sensitivity troponin I assay that has greater precision at very low concentrations compared with the contemporary assay. The limit of detection is 1.2 ng/L and the inter-assay coefficient of variation <10% at 4.7 ng/L. The upper reference limit (99th percentile) based on 4,590 samples from healthy men and women is 34 ng/L for men and 16 ng/L for women.

7.2.4 Positron Emission and Computed Tomography Coronary Angiography

Study scans will be performed in the Clinical Research Imaging Centre.

Patients with a heart rate exceeding 65 beats/min may receive intravenous or oral beta-blockade (e.g. 5 to 100 mg metoprolol) 1 h before computed tomography. All patients will receive sublingual glyceryl trinitrate (200-400 μ g) just prior to the computed tomography coronary angiography.

All patients will undergo dual cardiac and respiratory-gated positron emission and computed tomography imaging of the coronary arteries with a hybrid scanner (64-multidetector Biograph mCT, Siemens Medical Systems, Erlangen, Germany). Study subjects will be administered a target dose of 250 MBq 18F-fluoride intravenously and subsequently rested in a quiet environment for 60 min. An attenuation correction computed tomography scan (non-enhanced 120 kV and 50 mA) will then be performed, followed by positron emission tomography imaging of the thorax in list-mode for 30 min.

Computed tomography coronary calcium score and angiography will be undertaken in the same visit as the 18F-fluoride scan and again at 1 year. With the patient lying still on the scanner after acquisition of the positron emission tomography scan, an electrocardiogram-gated breath-hold computed tomography scan (non-contrast-enhanced, 40 mAs/rotation, 120 kV; CareDose, Siemens Medical Systems) of the coronary arteries will be performed at the following settings: 330 ms rotation time, 100 (body mass index [BMI] <25 kg/m²) or 120 (body mass index >25 kg/m²) kV tube voltage, 160-245 mAs tube current, 3.8 mm/rotation table feed, prospective (heart rate regular and <60/min), or retrospective (heart rate >60 /min) electrocardiogram-gated. Depending on the BMI, a bolus of 80-100 mL of contrast (400 mgI/mL; Iomeron, Bracco, Milan, Italy) will be injected intravenously at 5 mL/s, after determining the appropriate trigger delay with a test bolus of 20 mL contrast material.

The positron emission tomography scans will be reconstructed in multiple phases of the cardiac cycle, with the diastolic phase (50-75%) used for analysis. The computed tomography coronary angiography scans will be reconstructed at 0.75 x 0.7 mm and 0.6 x 0.3 mm for retrospective and prospective acquisitions respectively at 60%, 65% and 70% of the cardiac cycle. Additional reconstructions will be undertaken as necessary. Positron emission tomography scans will correct for cardiac motion correction using electrocardiogram-gated images.

18F-F PET Natural History Sub-study

Using the same scan process as outlined above a sub-group of patients will be selected for 1 additional PET scan. In total this will involve 80 patients out of the total cohort. The first 20 participants to be scanned will be to assess the reproducibility of 18F-fluoride uptake and will undergo a second PET scan at the randomisation visit (1 week after the baseline scan). This group will comprise 10 patients from both of the PET positive and PET negative samples. Following this we will investigate the natural history of 18F-fluoride uptake by performing repeat PET scans on 60 patients in total from the initial PET positive sample with 20 patients scanned at the 3 month, 6 month and 12 month follow up visits. No individual patient will undergo more than 2 PET scans during the course of the study. In order to allow accurate co-registration of images, repeat CT coronary angiograms will be performed at the time of the repeat PET scans. The additional PET scan for those in the sub-study will be performed at the 1 week, 3 month, 6 month or 12 month visit but the additional CTCA scan will only be performed at 1 week, 3 month or 6 month visits as the CTCA scan at 12 months will be performed on all participants irrespective of whether they are taking part in the sub-study

7.2.5 Platelet-Monocyte Aggregates

The effect of ticagrelor on platelet activation will be assessed before and after *in vitro* stimulation with 20 μ M adenosine diphosphate to assess inhibition of the P2Y₁₂ receptor [Harding *et al*, 2007; Burdess *et al*, 2010; Frehling *et al* 2011]. This will be performed at the baseline visit (before study medication ingestion) and at the 30 day visit [Gurbel *et al* 2009; Frehling *et al* 2011]. Platelet-monocyte aggregate measurements will be performed by a trained technician independent to the study team to ensure blinding of treatment allocation is not compromised.

Blood will be anticoagulated with D-phenylalanyl-L-prolyl-L-arginine chloromethylketone (PPACK; Cambridge Biosciences, UK). Five minutes after sample collection, samples will be stained with the following conjugated monoclonal antibodies: APC-conjugated CD14 (Becton-Dickinson, UK);, PE-conjugated CD62P (Becton-Dickinson, UK); PE-Cy7-conjugated CD11b(Becton-Dickinson, UK); FITC-conjugated CD42a(Becton-Dickinson, UK); and appropriate control samples prepared. Once stained, samples will be incubated for 20 min at room temperature and fixed with FACS-Lyse (PMA analysis) or paraformaldehyde (platelet analysis). Samples will be analyzed using a FACScalibur flow cytometer (Becton-Dickinson, UK). Platelet-monocyte aggregates will be defined as monocytes staining positive for CD42a, as described previously [Harding *et al*, 2007]. Analysis will be performed using FlowJo (Treestar, USA).

7.2.6 Biological Samples

Blood samples will be collected and tested at baseline, 30 days and 3, 6, 9 and 12 months. At baseline, blood samples will be taken for routine clinical biochemistry and haematology (including full blood count, urea, creatinine and electrolytes, liver function tests, total cholesterol and glucose).

Approximately 20 mL of blood will be obtained on each visit except that an additional 20 mL will be taken at baseline for the clinical biochemistry and haematology assessments. Blood will also be stored for DNA extraction for subsequent analysis as appropriate.

Blood samples will be processed and stored in the Clinical Research Facility. Blood sample will be processed (plasma and serum) and stored at -80°C for later analysis of potential extracellular matrix and inflammatory biomarkers. Blood will also undergo DNA extraction and flow cytometric assessment for platelet monocyte aggregates [Burdess *et al*, 2010].

All samples will be stored in locked secure freezers and in compliance with the sponsor's tissue governance policies.

All samples will be retained unless consent is withdrawn by the participant who specifically requests that their samples are destroyed.

8 DATA COLLECTION

All trial data will be recorded onto written case record forms (CRF) by a member of the research team and then entered into electronic CRFs designed and developed by the Edinburgh Clinical Trials Unit.

9 STATISTICS AND DATA ANALYSIS

9.1 SAMPLE SIZE CALCULATION

Patients with increased ¹⁸F-fluoride activity had plasma high-sensitivity troponin concentrations that were more than double those of patients without increased ¹⁸F-fluoride uptake (7.89 ± 9.34 versus 3.10 ± 1.89 ng/L; $P=0.047$) in our recent trial [Joshi et al, 2013]. Based upon the assumption that ticagrelor will reduce plasma high sensitivity troponin concentrations by one half (i.e from 7.89 to 3.95 ng/L, with standard deviations of 9.34 and 1.89 respectively), we will require 48 patients per treatment arm at 80% power and two-sided $P<0.05$. Allowance for missing data brings this to 55 per group. Following review of the first 170 PET scans within the DIAMOND study, the proportion of patients who demonstrate coronary tracer uptake is 60%. Consequently we will need 183 patients with follow-up data available for the primary endpoint. In order to allow for participant withdrawal prior to the 30-day visit we will recruit a total of 220 patients.

The Edinburgh Heart Centre performs more than 5,000 diagnostic angiograms and 2,500 angioplasty procedures per year. This should allow an adequate pool of potentially suitable patients with angiographically proven stable coronary artery disease from which to recruit.

9.2 PROPOSED ANALYSES

9.2.1 Description of Analysis Sets

The primary analysis will be to determine whether ticagrelor will reduce plasma high-sensitivity troponin concentrations compared with placebo in patients with stable coronary heart disease and increased coronary ¹⁸F-fluoride uptake. For this primary analysis, we will exclude any patient who does not have a blood sample for estimation of the one-month plasma troponin concentration or whose compliance is deemed inadequate (as estimated from pill counts). The required level of medication compliance will be described in the statistical analysis plan.

9.2.2 Methods of Statistical Analysis

For the primary analysis, the change in plasma high-sensitivity troponin concentration from baseline to 30 days will be compared between the two treatment groups (ticagrelor and placebo) using linear regression, adjusting for the minimisation variables, in patients with coronary ¹⁸F-fluoride uptake. Prior to analysis, tests for normality will be undertaken and, where data are skewed, logarithmic transformation will be considered prior to analysis. Effect sizes and 95% confidence intervals will be calculated. Similar analyses will be performed for the assessment of troponin at 30 days in patients without coronary ¹⁸F-fluoride uptake, and in the study population as a whole; for troponin at 1 year; and for calcium score and plaque volume at 1 year at the site of baseline coronary ¹⁸F-fluoride uptake.

Statistical analysis will be performed using SAS. A two-sided $P<0.05$ will be taken as statistically significant. A full statistical analysis plan will be documented prior to data base lock. This will be overseen by the trial statistician in the Edinburgh Clinical Trials Unit.

10 ADVERSE EVENTS

The Investigator is responsible for the detection and documentation of events meeting the criteria and definitions detailed below.

Full details of contraindications and side effects that have been reported following administration of the IMP can be found in the relevant Summary of Product Characteristics (SmPC).

Participants will be instructed to contact their Investigator at any time after consenting to join the trial if any symptoms develop. All adverse events (AE) that occur after joining the trial must be reported in detail in the Case Report Form (CRF) or AE form. In the case of an AE, the Investigator should initiate the appropriate treatment according to their medical judgment. After initially recording an AE, the Investigator should follow each AE until resolution of the event or until no longer medically indicated.

10.1 DEFINITIONS

An **adverse event** (AE) is any untoward medical occurrence in a clinical trial participant which does not necessarily have a causal relationship with an investigational medicinal product (IMP).

An **adverse reaction** (AR) is any untoward and unintended response to an IMP which is related to any dose administered to that participant.

A **serious adverse event** (SAE), **serious adverse reaction** (SAR). Any AE or AR that at any dose:

- results in death of the clinical trial participant;
- is life threatening*;
- requires in-patient hospitalisation[^] or prolongation of existing hospitalisation;
- results in persistent or significant disability or incapacity;
- consists of a congenital anomaly or birth defect;
- results in any other significant medical event not meeting the criteria above.

*Life-threatening in the definition of an SAE or SAR refers to an event where the participant was at risk of death at the time of the event. It does not refer to an event which hypothetically might have caused death if it were more severe.

[^]Any hospitalisation that was planned prior to randomisation will not meet SAE criteria. Any hospitalisation that is planned post randomisation will meet the SAE criteria.

A suspected unexpected serious adverse reaction (SUSAR) is any AR that is classified as serious and is suspected to be caused by the IMP, that it is not consistent with the information about the IMP in the Summary of Product Characteristics (SmPC) or Investigators Brochure.

10.2 IDENTIFYING AEs AND SAEs

All AEs and SAEs will be recorded from the time a participant signs the consent form to take part in the study until the last study visit.

Participants will be asked about the occurrence of AEs/SAEs at every visit during the study. Open-ended and non-leading verbal questioning of the participant will be used to enquire about AE/SAE occurrence. Participants will also be asked if they have been admitted to hospital, had any accidents, used any new medicines or changed concomitant medication regimens. If there is any doubt as to whether a clinical observation is an AE, the event will be recorded.

AEs and SAEs may also be identified via information from support departments e.g. laboratories.

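### Protocol 10.2 asks about adverse events at every visit, but the visit table schedules no enquiry at randomisation, and SAP 7.6 has no rule for events that start before first dose

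*Protocol*

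**What the plan says.** **Text.** Protocol 10.2 has events recorded from consent through to the final visit. It adds "Participants will be asked about the occurrence of AEs/SAEs at every visit during the study", and says participants are also asked about new medicines and changed regimens. Section 7 defines the visits: "Trial participants will undergo 8 study visits: screening visit, baseline, randomisation and after 1, 3, 6, 9 and 12 months".

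**Table.** In the visit table in Protocol 7.2, the row "AE/SAE Reporting" is marked at baseline, 30 days, 3, 6 and 9 months and 1 year. It is blank at screening and at randomisation. The concomitant medications row has the same two blanks. A continuing-eligibility check and drug dispensing are marked at randomisation.

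**Timing and scans.** The baseline column is headed "Baseline (-15 days ±10 days" (closing bracket omitted), and the text above the table says "The randomisation visit must be conducted within 25 days of the baseline visit". On scanning, 7.2.4 says "Computed tomography coronary calcium score and angiography will be undertaken in the same visit as the 18F-fluoride scan and again at 1 year". For the 20 reproducibility patients it says they "will undergo a second PET scan at the randomisation visit (1 week after the baseline scan"), with a CT angiogram repeated alongside each repeat PET.

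**Analysis.** SAP 7.6 summarises AEs in the safety population by treatment received, plans no formal test, and does not refer to onset relative to first dose.

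**The concern.** Two parts of the protocol give different instructions for the last contact before study drug starts. The text requires an AE and medication enquiry there; the table does not schedule one. Staff tend to work from the table, and case record forms are often laid out from it.

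If the table is followed, the period after the baseline scan is first covered by a scheduled enquiry at the 30-day visit, together with the first weeks on drug. Participants then have to recall whether something began before or after the first tablet. In the reproducibility sub-study, no AE enquiry is scheduled between the baseline CT angiogram and its repeat.

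The SAP adds a separate problem. Recording starts at consent and the tables are by treatment received, so an event known to have started before first dose is still tabulated under ticagrelor or placebo. Such events cannot be caused by the drug and should occur about equally in both arms, which pulls the descriptive comparison towards no difference. Safety and tolerability is a stated objective (Protocol 2.1.3). No data monitoring committee is convened (12.3), so these descriptive tables are the main trial-level summary of safety.

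**Working it through.** **1. Visits.** Section 7 states 8: screening, baseline and randomisation (3) plus 1, 3, 6, 9 and 12 months (5); 3 + 5 = 8. The table has 8 visit columns, so the count reproduces.

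**2. Is the blank real?** Neighbouring rows fall where they should. Dispensing is at randomisation, 3, 6 and 9 months, and compliance checks start at 30 days. The columns are therefore aligned and the blank is not an artefact of text extraction.

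**3. Enquiries required and scheduled.** Section 10.2 implies 8; the AE row marks 6. Screening and randomisation are missing.

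**4. Interval if the table is followed.** Baseline is 15 ± 10 days before Day 0, so 5 to 25 days before. The upper end, 15 + 10 = 25, reproduces the stated 25-day limit. The first follow-up is 30 ± 5 days after Day 0, so 25 to 35 days after.

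| | Baseline to Day 0 | Day 0 to first follow-up | Total |
|---|---|---|---|
| Shortest | 5 | 25 | 30 days |
| Nominal | 15 | 30 | 45 days |
| Longest | 25 | 35 | 60 days |

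With an enquiry at randomisation, the wait after the baseline visit becomes 5 to 25 days (nominally 15), all of it before study drug.

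**5. Effect on the AE tables.** Assumptions: drug starts on Day 0; 365 days on drug; a constant background AE rate, equal in both arms before dosing; a true on-drug rate ratio of 2; every event between baseline and Day 0 counted in the arm tables.

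Pre-dose share s = pre-dose days / (pre-dose days + 365). Apparent ratio = s + 2(1 − s) = 2 − s.

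| Pre-dose days | s | Apparent ratio |
|---|---|---|
| 5 | 5/370 = 1.4% | 1.99 |
| 15 | 15/380 = 3.9% | 1.96 |
| 25 | 25/390 = 6.4% | 1.94 |

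This covers only the interval from baseline to first dose. Events between consent and baseline would also be pooled under SAP 7.6. The table heads the screening column −183 days but does not say how far apart consent and baseline usually fall, so I put no figure on that part.

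**The case against.** The strongest reply is that nothing need go wrong. Section 10.2 already requires the enquiry at randomisation, and a single centre can follow it. Other safeguards exist:

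- The baseline visit carries an AE mark, so an immediate scan reaction can be caught.
- Continuing eligibility is confirmed at randomisation. The exclusion criteria include contraindication to iodinated contrast, active bleeding and several prohibited medicines.
- Participants are told to report symptoms at any time after consent (Protocol 10), and laboratories can identify events (10.2).
- Onset date is recorded for each event (10.3).
- SAP 7.6 plans no test, and Protocol 7.1 says there are no pre-specified safety outcome measures.

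Most of this stands, and it is why the point is minor. It does not remove it. An eligibility check is not an open AE enquiry. Spontaneous reporting supplements the scheduled questions and does not replace them. The table schedules no biochemistry between baseline and 9 months, so routine laboratory follow-up would not show early kidney impairment, which Protocol 12.6.2 names as a contrast risk. Onset dates help only if the analysis uses them, and SAP 7.6 does not say that it will.

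Three stronger readings are tempting and are not supported:

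- *All 220 patients will go unasked until 30 days.* This follows only if the table prevails over 10.2.
- *The first-month drug comparison is heavily diluted.* SAP 7.6 has no first-month AE comparison; its summary has no time restriction.
- *The bleeding comparison is compromised.* The contrast risks named in 12.6.2 are allergic reactions and kidney impairment. SAP 7.6.1 reports time to each bleed from study entry, defined in SAP 7 as the randomisation date, so a correctly dated pre-dose bleed is visible.

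**Conclusion.** The point holds as a contradiction between text and table, together with a gap in the SAP. Section 10.2 calls for 8 enquiries and the table schedules 6; one of the two missing is the last visit before study drug. If the table is followed, the first scheduled enquiry after the baseline scan visit is 30 to 60 days later, of which 5 to 25 days are pre-drug. Whether staff would follow the table cannot be settled from the documents.

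The SAP gap does not depend on that: without a rule on onset, pre-dose events enter the arm tables however well they are dated. Under the deliberately pessimistic assumptions above, a true doubling would appear as 1.94 to 1.99 because of events between baseline and first dose. Only descriptive safety reporting is touched; the primary endpoint, sample size and significance level are not. Severity is low, but the correction is cheap enough to make.

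**What to change.** 1. Reconcile the Protocol 7.2 table with 10.2. Mark AE/SAE reporting and concomitant medications at randomisation, to be completed before first dose and, in the reproducibility sub-study, before the repeat scan. Mark AE/SAE reporting from consent, so that the screening column agrees with the stated recording period.
2. Add a sentence to SAP 7.6: events with onset before first dose are listed separately and excluded from the by-treatment summaries.

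Both are needed. The table change alone would not keep pre-dose events out of the arm tables, because SAP 7.6 has no pre-treatment category. The SAP sentence alone would rely on onset dates recalled at 30 days if staff follow the table.

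The cost is a minor amendment to the table, one case record form page at a visit that already takes place (a few minutes per patient) and one SAP sentence.
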